12.1 Subject Disposition

Participant disposition will be summarized for all enrolled participants. The summary including the number and percentage (based on total number of participants enrolled) of participants in each of the following categories will be prepared:

- Completing 12-month blinded assessment based on the ITT population
- Early Termination based on the ITT population
- Safety population, ITT, mITT, and PP populations

A Participant is considered to have completed the study if the Participant completes the Day 365 Visit and has at least 5 days of the most recent 7 days with electronic diary (eDiary) entries prior to the Day 365 Visit. Major protocol deviations for participants not in the PP populations will be listed. Major protocol deviations will be summarized for the ITT population.

12.2 Demographic and Baseline Characteristics

The following outcomes will be summarized by the standard methods for continuous and categorical variables described in Section 8.1.

The demographics include the following parameters:

- Age at informed consent of main study
- Sex
- Race
- Ethnicity
- Vital signs: height, weight, BMI,

The baseline characteristics include the following:

- Baseline Average Daily Pain Score from the 7 days prior to the Day 0 Visit obtained from the BPI-DPN eDiary
- Vital signs: blood pressure, heart rate, respiration rate, temperature
- Diabetes type
- 12-lead electrocardiogram (ECG): Normal, Abnormal Not Clinically Significant (NCS), Abnormal Clinically Significant (CS)

These parameters will be summarized by treatment group for the ITT and included in data listings. The demographic and selected baseline characteristics (diabetes type and specific medical history items of interest) will also be summarized for each level of the stratification variable.

12.3 Prior and Concomitant Medications

Prior medications are those with a stop date before the first day of treatment during main study (VMDN-003-2) or have missing stop date but are not marked as ongoing. Concomitant medications are those medications taken after the initial dose of study drug in the main study (VMDN-003-2). A medication with a missing start date and a stop date that is either missing or on or after the treatment start date will be considered as concomitant. All prior and concomitant medications will be assigned WHO drug names using the WHO Drug Dictionary (March 2018 version or later). Prior and concomitant medications will be summarized separately for each treatment group by preferred names. These summaries will present the number and percentage of participants using each medication.

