12.5.1.1 Sensitivity Analyses

The primary endpoint will be also analyzed for mITT and PP using the same continuous Repeated Measure Model described in [Section 12.5.1](#).

In addition, there will be a sensitivity analysis accounting for the individual pain scores influenced by the protocol-prohibited concomitant medications. In this analysis, the pain scores after receiving protocol-prohibited concomitant medication will be replaced with the baseline value only if a prohibited medication was used during the 10 days prior to Day 90 visit, Day 180 visit, Day 270 visit or Day 365 visit.

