12.5.2.3 Other Analysis of the Secondary Efficacy Endpoints

The secondary endpoints (not including PGIC endpoints) will be also analyzed for mITT and PP using the same analysis method described in Section 12.5.1. PGIC endpoint will be summarized by treatment group.

In addition, there will be a sensitivity analysis accounting for the individual pain scores influenced by the protocol-prohibited concomitant medications. In this analysis, the pain scores after receiving protocol-prohibited concomitant medication will be replaced with the baseline value only if a prohibited medication was used during the 10 days prior to Day 90 visit, Day 180 visit, Day 270 visit or the Day 365 visit.

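### The prior-medication rule in SAP 12.3 ignores the start date, so some on-study drugs are both prior and concomitant with no rule to decide between them

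*SAP*

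**What the plan says.** SAP 12.3 sorts medications with three sentences.

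- **Prior.** The stop date falls before the first treatment day of the main study, "or have missing stop date but are not marked as ongoing". Neither limb refers to the start date.
- **Concomitant.** "Concomitant medications are those medications taken after the initial dose of study drug in the main study (VMDN-003-2". There is no condition on the stop date.
- **Missing start date.** "A medication with a missing start date and a stop date that is either missing or on or after the treatment start date" is concomitant.

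The two classes are then tabulated separately. Nothing says that they exclude each other or which one takes precedence.

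SAP 12.5.1.1 plans a sensitivity analysis of the primary endpoint "accounting for the individual pain scores influenced by the protocol-prohibited concomitant medications". A score "will be replaced with the baseline value only if a prohibited medication was used during the 10 days prior to Day 90 visit", and the same window applies before Days 180, 270 and 365. SAP 12.5.2.3 repeats the rule for the secondary endpoints. Neither section cites 12.3 or says what to do when the stop date is unknown.

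**The concern.** The second limb of the prior definition turns an incomplete end-of-use entry into evidence that use ended before the trial began. When the recorded start is after first dose, that inference is false on its face.

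Two outputs are at stake. The first is descriptive: on-study drugs can appear in the prior-medication table. The second is the prohibited-medication sensitivity analysis, which is worded in terms of concomitant medication: "the pain scores after receiving protocol-prohibited concomitant medication will be replaced with the baseline value". SAP 12.3 is the only place where that term is defined. If records are first split into exclusive classes with prior taking precedence, a prohibited drug used on study never reaches the step that resets the score. A pain score that the drug may have lowered then stays in the very analysis meant to remove it. Two programmers could each follow 12.3 faithfully and produce different concomitant sets.

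**Working it through.** The plan gives no figure to reproduce, so the check applies the three sentences literally to every kind of record.

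**Cases.** Start date: missing, before first dose, or after it. For each start there are four end-of-use entries: stop missing and not ongoing; stop missing and ongoing; stop before first dose; stop on or after first dose. That gives 3 × 4 = 12 combinations. One is impossible (start after first dose, stop before it), which leaves 11.

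**Result.** Eight of the 11 fall cleanly into one class: 2 prior (stop before first dose) and 6 concomitant. The other three are the cases in which the second limb acts:

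| Start | Stop | Ongoing | Prior? | Concomitant? | After the fix |
|---|---|---|---|---|---|
| After first dose | Missing | No | Yes, second limb | Yes, second sentence | Concomitant |
| Missing | Missing | No | Yes, second limb | Yes, third sentence | Concomitant |
| Before first dose | Missing | No | Yes, second limb | Cannot be told | Concomitant by default |

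Two of the 11 cases are contradictory as written. After the fix none is, and the split is 2 prior and 6 + 3 = 9 concomitant.

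**Does another section resolve it?**

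- SAP 10.6.3 says that wholly missing concomitant-medication dates are not imputed. Its Table 1 has no rule for a wholly missing stop date, and its imputed partial dates are stated to be for deriving duration, not for classification.
- SAP 10.0 sends questionable values to the CDRC but gives it no classification rule.
- Protocol 1.3 (footnote 9) asks for a stop date or an ongoing mark. The clause in SAP 12.3 itself anticipates records with neither.
- SAP 12.6.1 treats an adverse event with both dates missing as treatment-emergent. That default, like the third sentence of 12.3, counts the unknown as on-study. The second limb of prior does the reverse.

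**Effect on the 10-day window.** Take two prohibited drugs, each with no stop date and no ongoing mark.

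- *Start on Day 360, visit on Day 365.* The start is 365 − 360 = 5 days before the visit, so use within the window is established whatever the stop date. The trigger is met unless the record has already been removed as prior.
- *Start on Day 200, visit on Day 270.* The start is 270 − 200 = 70 days before the visit. Whether use continued into the last 10 days is unknown. Classing the drug as concomitant does not settle this, and the SAP has no rule for it.

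**Size.** If *k* participants in an arm of *n* each keep a score that lies *d* points below baseline, the arm's raw mean change differs by *k* × *d* / *n* from what the reset rule would give. The documents supply none of the three quantities.

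**The case against.** The strongest reply is that the text does not remove anything from the concomitant set. The second sentence of 12.3 makes every drug taken after first dose concomitant, whatever its stop date. The trigger in 12.5.1.1 and 12.5.2.3 is that "the pain scores after receiving protocol-prohibited concomitant medication will be replaced with the baseline value only if a prohibited medication was used" within the window, with no reference to 12.3. A programmer working from the raw medication records would catch the Day 360 drug. This stands, and it rules out a stronger reading that a reader might draw: that such drugs are simply classified as prior and so drop out of the sensitivity analysis. Drop-out needs an extra step, prior overriding concomitant, which the SAP neither instructs nor excludes.

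A second reply is that such records should be rare at lock. Missing data go back to the sites (Protocol 10.1.6.3), edit checks apply (10.1.7), and lock requires that no queries are outstanding (10.1.6.5). This is fair on frequency, but it does not repair a rule written for exactly those records.

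A third reply concerns the obvious remedy of treating every missing stop date as ongoing. That would carry a short course begun around Day 200 through the windows before both Day 270 and Day 365, and reset both scores to baseline without evidence of use. This stands too, and the fix below avoids it.

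**Conclusion.** The rule is wrong as written, with low impact. Two of 11 possible record types receive contradictory classes, and the literal text places on-study drugs in the prior-medication table. That much needs no assumption.

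The effect on the concomitant table and on the two sensitivity analyses is conditional: it arises only if prior is programmed to override. A separate gap, the lack of any rule for an unknown stop date in the 10-day window, remains under either classification unless the start date itself falls in the window.

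A reader might infer that the primary result is at risk, or try to put a number of pain-scale points on the bias. The documents support neither. The primary model in SAP 12.5.1 does not use medication class. No count of affected records, no arm size and no size of score change for such participants is given. Any shift would reach the treatment difference only if the affected records, or their score changes, differed between arms, and nothing in the documents suggests that they would.

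**What to change.** In SAP 12.3:

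- Delete the clause that makes a record prior because its stop date is missing and it is not marked ongoing.
- Define prior as a stop date before first dose in the main study.
- Class as concomitant any drug with a start date on or after first dose, and any record with both dates missing.
- State that the two classes are exclusive and that concomitant is the default.

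Under this default, a drug started before first dose with no stop date and no ongoing mark moves from prior to concomitant. Such records should be queried before lock so that finished pre-study use is not counted as on-study.

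In SAP 12.5.1.1 and 12.5.2.3, add that an unknown stop date is not automatically carried forward as ongoing. For each such record of a prohibited drug, the blinded CDRC decides before database lock whether use fell in the 10 days before each visit, and the decision is documented.

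The cost is a rewrite of a few lines in 12.3, one added sentence in each of the two sensitivity sections, and one listing for a committee that already reviews data blinded before lock. Data collection and the primary analysis do not change.

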12.4 Important Protocol Deviations

A Clinical data Review Committee (CDRC) will review all subjects to evaluate whether subjects meet major protocol eligibility criteria prior to database lock and breaking the randomization codes.

12.5 Efficacy Analyses

12.5.1 Primary Analysis of the Primary Efficacy Endpoint

The primary analysis for comparing the change in mean Average Daily Pain Scores at the Day 365 visit from Baseline between the treatment groups will be analyzed using the MI method for handling the missing data as specified in Section 10.6.1. A linear mixed-effects model for repeated measures (hereinafter, the continuous Repeated Measures Model) will be used to analyze each complete dataset. The model will include treatment, visit (Day 90 and Day 180 from main study, Day 270 and 365 from extension study), treatment-by-visit interaction, and baseline (Study VMDN-003-2) Average Daily Pain Score as a covariate using an unstructured variance-covariance matrix. Then the Proc MIANALYZE procedures will be used to generate the point estimate for the least-squares mean of the treatment difference (Engensis – Placebo)

and the corresponding 95% confidence interval. LSMEANS, differences and p values compared to baseline will be presented for Day 90 and Day 180 visits from the main study, and Day 270 and Day 365 at the extension study.

The SAS code to be used to for the continuous repeated measure model is presented below:

```
proc mixed data=work order=internal method = REML;
class usubjid trtp avisitn;
model chg = trtp avisitn trtp*avisitn base / ddfm=KR;
repeated avisitn /subject = usubjid type = un;
lsmeans trtp trtp*avisitn / pdiff cl;
run;
```

where

USUBJID: subject ID TRTP: treatment

AVISITN: variable representing visits

CHG: change in the Average Daily Pain Score from baseline(Study VMDN-003-2)

BASE: baseline (Study VMDN-003-2) Average Daily Pain Score (continuous variable)

Other variance-covariance structures selected from among compound symmetry, Toeplitz, and autoregressive (1) options will be substituted based on the lowest Akaike information criterion (AIC) if convergence problems arise.

The primary efficacy analysis will be performed for ITT population.

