6.1.2. Stratification

There will be no stratification of Participants in the VMDN-003-2b extension study as all Participants who are entered into the VMDN-003-2b extension study are to continue in the stratification they were assigned in the VMDN-003-2 study.

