10.6.1 Missing Pain Scores for the Average Scores from BPI-DPN

The means of the Average Daily Pain Scores (Question 5 from the BPI-DPN) for a visit will be considered as missing if fewer than 5 of 7 days of BPI-DPN eDiary entries are provided. Any missing mean pain score of ADPS will be imputed using the methods described below.

Multiple Imputation (MI) method:

- Step 1: Intermittent missing values will first be imputed by treatment group using the Markov Chain Monte Carlo (MCMC) method, resulting in data with a monotone pattern.
- Step 2: Multiple imputation by treatment group using linear mixed model regression with factors of baseline pain score, baseline HbA1c, gender, and age at informed consent (Study VMDN-003-2) will be applied to the data obtained from the MCMC step. The imputed score will be rounded to the first decimal point.

The entire procedure will be repeated 10 times, and 10 complete datasets will be used for the analysis.

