12.5.2 Analysis of the Secondary Efficacy Endpoints

12.5.2.1 Change from Baseline in the means of Worst Pain Scores at Day 365 Visit

The change from Baseline (Study VMDN-003-2) in mean worst pain score at the Day 365 visit will be analyzed using the same linear mixed method described in Section 8.4.1 for the ITT population. Missing data will be handled according to the method pre-specified in [Section 12.5.1](#)

12.5.2.2 Proportion of Responders (≥50% reduction in mean ADPS) on Day 365

Responders will be defined as participants with at least 50% reduction from Baseline in the mean ADPS at the Day 365 visit. The percent reduction will be computed as follows:

$$\%Change = \frac{Day\ 365\ mean\ ADPS - Baseline\ mean\ ADPS}{Baseline\ mean\ ADPS} \times 100$$

For each 10 completed datasets imputed using the MI method, a generalized linear mixed-effects model for repeated measures based on a logit link function (hereinafter, the categorical Repeated Measures Model) will be used for comparing the percentage of responders between the two study treatment groups. The model will include treatment, visit, treatment-by-visit interaction, and baseline (Study VMDN-003-2) Average Daily Pain Score as covariates with an unstructured variance-covariance matrix. Then the Proc MIANALYZE procedures will be used to generate the point estimate and the corresponding 95% confidence interval. Study visits from main study will include Baseline and Day 180 and extension study Day 270 and Day 365 will be included.

The SAS code to be used to conduct the analysis is presented below:

```
PROC GLIMMIX DATA=work method=REML;
class usubjid trtp avisitn;
MODEL critvar(event='Y') = trtp base avisitn trtp*avisitn / DIST=binary LINK=LOGIT SOLUTION;
random INTERCEPT / SUBJECT=usubjid type=un;
lsmeans trtp *avisitn / diff cl; RUN;
```

where

USUBJID: subject ID TRTP: treatment

AVISITN: variable representing visits

CHG: change in Average Daily Pain Score from baseline(Study VMDN-003-2)

BASE: (Study VMDN-003-2) Average Daily Pain Score (continuous variable)

CRITVAR: a Y/N variable indicating if the participant had at least a 50% reduction in Average Daily Pain Score from baseline (Study VMDN-003-2) at that visit

Other variance-covariance structures selected from among compound symmetry, Toeplitz, and autoregressive (1) options will be substituted based on the lowest AIC if convergence problems arise.

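### The stratification factor carried over from VMDN-003-2 is unnamed and not identified in any main efficacy model; the likely cost is a modest loss of precision, not invalidity

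*SAP*

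**What the plan says.** Protocol 6.1.2 says that extension participants "are to continue in the stratification they were assigned in the VMDN-003-2 study". The SAP treats the factor as data in hand. In 12.2, demographic and selected baseline characteristics "will also be summarized for each level of the stratification variable", and 12.6.1 splits the AESI tables by it too.

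The models read as follows:

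- **Primary (SAP 12.5.1).** The text lists treatment, visit, "treatment-by-visit interaction, and baseline (Study VMDN-003-2) Average Daily Pain Score as a covariate using an unstructured variance-covariance matrix". The code agrees: "model chg = trtp avisitn trtp*avisitn base / ddfm=KR".
- **Worst pain (12.5.2.1).** The endpoint "will be analyzed using the same linear mixed method described in Section 8.4.1 for the ITT population". This SAP has no section of that number; the evident target is 12.5.1.
- **Responders (12.5.2.2).** The code is "MODEL critvar(event='Y') = trtp base avisitn trtp*avisitn", with "random INTERCEPT / SUBJECT=usubjid type=un".
- **Imputation Step 2 (10.6.1).** It uses "linear mixed model regression with factors of baseline pain score, baseline HbA1c, gender, and age at informed consent (Study VMDN-003-2".

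SAP 12.5.3 lists the same four variables (baseline pain, HbA1c, gender, age) as subgroup factors and fits subgroup and interaction models with them. None of the four is labelled as the stratification factor. Only baseline pain is in the main efficacy models.

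**The concern.** Randomising within strata makes the arms more alike on the stratification factor than chance would. A linear model that omits the factor does not credit that balance: variation between strata stays in the residual, and the reported standard error describes a less well balanced trial than the one that was run. If the factor is prognostic, confidence intervals are too wide and power is lost.

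Because the factor is not named, a reader cannot tell whether baseline ADPS already stands in for it or whether the main analysis ignores the stratification. If that is left open until the codes are broken, an adjusted analysis will look like a choice made after seeing the data.

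**Working it through.** **Inputs.** From the documents: two-sided 0.05 (SAP 12.0) and the model terms above. The documents give no sample size, SD, power, entry rate or prognostic strength (Protocol 9.1 and SAP 8.1 defer to VMDN-003-2 and to roll-over), so there is no planned figure to reproduce. Assumed: R2, the share of residual variance after baseline ADPS that the factor explains, at 0.02, 0.05 and 0.10; a proportion p of randomised participants entering the extension at random, at 1, 0.8 and 0.6; and 80% power under the adjusted model.

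**Formulas (linear models only).** Take the reported unadjusted SE as 1. Balanced strata remove their share R2 from the true variance. Random non-entry puts back (1 - p)R2, so the true SE is sqrt(1 - p·R2).

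- Reported SE / true SE = 1/sqrt(1 - p·R2)
- Size = 2·(1 - Phi(1.96/sqrt(1 - p·R2)))
- Power = Phi((2.8016·sqrt(1 - R2) - 1.96)/sqrt(1 - p·R2))

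For R2 = 0.10 and p = 1: 1/sqrt(0.90) = 1.054; size = 2·(1 - Phi(2.066)) = 0.039; power = Phi((2.6578 - 1.96)/0.9487) = Phi(0.736) = 0.769. At p = 0.6 the SE ratio is 1/sqrt(0.94) = 1.031.

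| R2 | SE excess, p = 1 / 0.8 / 0.6 | Size, p = 1 / 0.8 / 0.6 | Power, p = 1 / 0.6 |
|---|---|---|---|
| 0.02 | 1.0% / 0.8% / 0.6% | 0.048 / 0.048 / 0.049 | 79.4% / 79.3% |
| 0.05 | 2.6% / 2.1% / 1.5% | 0.044 / 0.046 / 0.047 | 78.5% / 78.3% |
| 0.10 | 5.4% / 4.3% / 3.1% | 0.039 / 0.041 / 0.043 | 76.9% / 76.4% |

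The power loss therefore runs from 80 - 79.4 = 0.6 to 80 - 76.4 = 3.6 points.

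**Simulation check.** A single-visit ANCOVA on baseline ADPS stood in for the Day 365 contrast, with two equal strata, 1:1 allocation within stratum, residual SD 2 and R2 0.10 (8,000 trials each). At full retention with N = 152, the SE was 0.3425 without the stratum and 0.3246 with it, and size was 0.040 and 0.050. At 60% random entry of 252, the SEs were 0.3442 and 0.3269 and size 0.046 and 0.049 (Monte Carlo SE 0.0024). When the stratum was a cut of baseline ADPS, the SEs were 0.3266 without and 0.3274 with it, a ratio of 0.998: no effect worth naming.

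**When balance fails.** The ITT set is formed at Day 180 from those who complete and consent (SAP 8.1, 9.1), so balance within strata is not assured. With R2 0.10, 80% mean entry of 188, and entry gaps running in opposite directions by arm across the two strata (5,000 trials, Monte Carlo SE about 0.003):

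| Gap (points) | Size, unadjusted | Size, adjusted |
|---|---|---|
| 10 | 0.043 | 0.043 |
| 15 | 0.052 | 0.047 |
| 20 | 0.066 | 0.053 |
| 30 | 0.098 | 0.049 |

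At 60% mean entry of 252, gaps of 10 and 20 points gave 0.056 and 0.087 unadjusted, against 0.048 and 0.043 adjusted.

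**The case against.** The strongest reply is that this is a request for clarification rather than a shown error. The stratification belongs to VMDN-003-2, whose protocol was not supplied, and parts of the SAP are redacted, so the factor may be named elsewhere. The analysis team must know it to produce the tables in 12.2 and 12.6.1. That stands: nothing here shows that the sponsor does not know the factor. But the main models are visible, and the primary and responder models appear in both prose and code. None of their terms is identified as the factor.

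It is also fair that 12.5.3 already examines efficacy by HbA1c, gender and age, one of which might be the factor. Those are subgroup and interaction models, however, and do not change the standard error of the main analysis. The power loss is measured against an assumed 80%, since the extension states no target.

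A reader might infer that the omission inflates the type I error. The calculations give size clearly above 5% only under large, opposite entry gaps by arm across strata. The documents do not suggest such gaps, and they keep the blind through the extension (Protocol 6.1.3, SAP 8.0). A reader might also infer a distorted responder odds ratio. The planned responder model has a subject random intercept, so the usual argument for a plain logistic model does not carry over directly, and no effect is claimed.

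**Conclusion.** The point holds as a modest, correctable weakness. No main efficacy model or imputation step identifies the factor within which participants were randomised, and the supplied text does not name it. If the factor predicts pain change beyond baseline ADPS and balance within strata survives roll-over, the primary and worst-pain analyses are slightly conservative, to the extent tabulated above. If the factor is a category of baseline ADPS, nothing material is lost.

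The sizes rest on assumed R2, entry and power and on a single-visit stand-in for the repeated-measures model. They do not cover the responder model or the imputation step. The adverse entry scenarios support adjusting as a safeguard against imbalance on this factor. They are not a prediction, and adjustment would not protect against selection on other variables.

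**What to change.** Before unblinding:

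1. Name the VMDN-003-2 stratification factor and its levels in the SAP.
2. Add it as a fixed effect to the 12.5.1 repeated-measures model, in text and PROC MIXED code, and to the worst-pain model.
3. For consistency, add it to the responder model and to 10.6.1 Step 2 if it is not already a predictor there. No gain is quantified for these two.
4. If it is a category of baseline ADPS, say instead that the continuous covariate covers it.

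No new data are needed. The price is one degree of freedom per extra stratum; the number of strata is not stated. With an assumed N of 160 and a factor of no prognostic value, 2 to 16 balanced strata changed the SE by less than 0.1%. With strata unbalanced by 60% random entry and about 160 analysed, the SE rose by about 0.1% (2 strata), 0.4% (4), 1% (8) and 2% (16). The last is close to the 2.6% excess at R2 0.05, so if there are many strata the SAP should state in advance a rule for pooling sparse ones.

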12.0 Statistical Methods

The primary analysis for this study will be performed and summarized after all randomized participants have had an opportunity to complete their 12-month follow-up visit.

The Safety Analysis will be based on the Safety population. The primary analyses of the efficacy endpoints will be based on the ITT population. Additional sensitivity analyses for the primary and secondary efficacy endpoints will be performed to further assess the effects of the treatment (Section 8.4.2 and 8.4.4).

The statistical analyses will be reported using summary tables, figures and listings. Continuous variables will be summarized with mean, standard deviation, median, minimum, maximum, 25th percentile, 75th percentile, and number of non-missing observations for each treatment group.

Categorical variables will be summarized by counts and by the percentage of participants in corresponding categories.

All inferential statistical analyses will be performed with a two-sided confidence level of 95% or a two-sided significance level of 0.05 unless otherwise noted.

All analyses and tabulations will be performed using SAS Version 9.4 or higher on a Server platform.

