12.5.3 Subgroup Analysis of Primary and Secondary Efficacy Endpoints

The subgroup analysis for the primary and secondary endpoints will be performed for the following factors:

- Baseline pain score of main study
- Baseline HbA1c of main study (< and ≥ median of main study)
- Gender (male and female)
- Age at informed consent (Study VMDN-003-2) (<65 years and ≥ 65 years)

For each subgroup of the ITT population, the primary and secondary endpoints will be summarized by treatment group and visit using descriptive statistics (n, mean, median, standard deviation, minimum, and maximum for the continuous variable and frequency and percentage for the categorical variable). Both types of descriptive summaries are also provided for the subgroups of study center and protocol version.

Participants will be assigned to a protocol version based on their randomization date and the date of Institutional Review Board (IRB) approval at their site.

The main analysis method described above for the primary and secondary endpoints will be used to analyze the treatment effect within each subgroup. Additionally, the possible treatment-by-subgroup interaction will be tested for each subgroup variable as follows:

- The interaction term for the subgroup variable and treatment group will be included in the analysis model. If the p-value of the interaction term is ≥ 0.05 , the treatment-by-subgroup interaction will be considered not statistically significant.

[REDACTED]

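### If the unstructured fit fails, every fallback covariance in SAP 12.5.1 forces one variance at all visits, so the Day 365 standard error is wrong whenever the Day 365 variance differs from the pooled variance

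*SAP*

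**What the plan says.** SAP 12.5.1 models change in mean Average Daily Pain Score with treatment, "visit (Day 90 and Day 180 from main study, Day 270 and 365 from extension study"), their interaction and the baseline score. The code requests an unstructured matrix, "repeated avisitn /subject = usubjid type = un", which gives each visit its own variance. Standard errors are model-based with DDFM=KR, and no empirical (sandwich) option appears.

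Missing means are multiply imputed ten times (SAP 10.6.1). On fitting, SAP 12.5.1 says: "A linear mixed-effects model for repeated measures (hereinafter, the continuous Repeated Measures Model) will be used to analyze each complete dataset". Results are pooled with PROC MIANALYZE. The fallback reads "Other variance-covariance structures selected from among compound symmetry, Toeplitz, and autoregressive (1) options will be substituted based on the lowest Akaike information criterion (AIC"), and the choice and trigger are "will be substituted based on the lowest Akaike information criterion (AIC) if convergence problems arise". No heterogeneous version is named, and nothing says whether one structure must be used across the ten datasets.

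The model is reused for the mITT and PP sensitivity analyses (12.5.1.1), worst pain (12.5.2.1) and subgroups, where "The main analysis method described above for the primary and secondary endpoints will be used to analyze the treatment effect within each subgroup". Section 12.5.2.2 repeats the fallback list for the binary responder model, which the calculation below does not cover.

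**The concern.** The primary contrast is at a single visit, Day 365, the last of the four. Under an unstructured matrix its standard error rests on the Day 365 variance. Under compound symmetry, Toeplitz or AR(1) it rests on one variance pooled over Days 90, 180, 270 and 365. AIC compares the three candidates on correlation pattern only and cannot detect or repair unequal variances. Kenward-Roger adjusts for estimating the parameters of the chosen structure, not for choosing the wrong one.

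If residual variance rises with time from baseline, the last visit is where a pooled variance understates it most. A fallback ought to preserve the error rate in the awkward case for which it is written.

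**Working it through.** **Inputs from the documents.** Two-sided 5% test (SAP 12.0: "two-sided significance level of 0.05 unless otherwise noted"), so the critical value is 1.960. Four visits, three fallback structures and model-based standard errors (SAP 12.5.1). Ten imputations (SAP 10.6.1). Neither document gives a sample size, an SD by visit, a correlation or a standard error for this study, so there is no planned figure to reproduce. The benchmark is the nominal 5%.

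**Assumed inputs.** Residual SDs at the four visits as in the table; correlation either exchangeable 0.7 or AR(1) 0.8.

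**Step 1, large sample.** Fit each structure to the assumed 4×4 covariance by Gaussian likelihood. Then

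- q = √(fitted Day 365 variance / true Day 365 variance)
- true type I error = 2 × [1 − Φ(1.960 × q)]

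For compound symmetry the fitted common variance is the mean of the four visit variances, so that column can be checked by hand. Example for SDs 1.8/1.9/2.0/2.1: (3.24 + 3.61 + 4.00 + 4.41)/4 = 3.815; q = √(3.815/4.41) = 0.930; 1.960 × 0.930 = 1.823; type I error = 0.068.

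| Assumed SDs, Days 90/180/270/365 | Mean variance | Day 365 variance | q (compound symmetry) | Type I error, all three structures |
|---|---|---|---|---|
| 2.0/2.0/2.0/2.0 | 4.000 | 4.00 | 1.000 | 5.0% |
| 1.8/2.2/2.2/2.2 (plateau) | 4.440 | 4.84 | 0.958 | 6.0–6.6% |
| 1.8/1.9/2.0/2.1 | 3.815 | 4.41 | 0.930 | 6.8% |
| 1.6/1.8/2.0/2.2 | 3.660 | 4.84 | 0.870 | 8.8% |
| 1.5/1.9/2.2/2.5 | 4.238 | 6.25 | 0.823 | 10.6–10.7% |
| 2.0/2.3/2.2/2.0 (hump) | 4.533 | 4.00 | 1.064 | 3.7–4.2% |
| 2.3/2.2/2.0/1.9 (falling) | 4.435 | 3.61 | 1.108 | 3.0% |

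**Step 2, simulation under no treatment effect.** Assumed 50 per arm, either with no missing data (4000 runs) or with 20% monotone dropout, ten imputations by arm and Rubin's rules (1500 runs). Compound symmetry and AR(1) were fitted; Toeplitz was assessed only in step 1.

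- Unstructured: 4.3–5.5% in all scenarios, nominal within simulation error.
- Fallback, equal SDs: 4.4–5.2%.
- Fallback, SDs 1.8 to 2.1: 6.2–7.2%.
- Fallback, SDs 1.6 to 2.2: 8.0–8.9%.
- Fallback, falling SDs: 2.7–3.1%.

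**Step 3, one structure or several.** Choosing by AIC separately in each imputed dataset and choosing once for all ten gave identical rejection rates in every scenario. This is unsurprising, since the candidates give nearly the same q.

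**Step 4, the remedy.** Heterogeneous Toeplitz and heterogeneous AR(1), fitted to the step 1 matrices (the 1.6/1.8/2.0/2.2 and hump patterns were not refitted), return the true Day 365 variance and 5.0%. Heterogeneous compound symmetry gives 5.0% under exchangeable correlation and 4.4% (q = 1.027) when the true correlation is AR(1) 0.8.

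**The case against.** The strongest reply is that the rule will probably never be used. It needs a convergence failure, and the model is fitted to complete imputed datasets with four visits and 4 × 5/2 = 10 covariance parameters. An unstructured fit to such data normally converges unless the sample is very small. This stands, and it is why the point is minor. It is weaker for the subgroup fits, which are smaller, and the documents fix no sample size (protocol 9.1, SAP 8.1).

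Second, rising variance is not shown. The outcome is a mean of at least five daily scores on a bounded 0–10 scale, the model adjusts for baseline, and the first modelled visit is already Day 90. A plateau is quite possible. The 10.6–10.7% figure needs a Day 365 variance 6.25/2.25 = 2.8 times that at Day 90. This stands too. A reader might infer that the fallback always makes the Day 365 standard error too small and takes type I error above 5%. The documents do not support that: with equal variances there is no error, and with a falling or humped pattern the test is conservative.

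Third, a reader might infer that choosing a structure separately per imputed dataset adds to the inflation. The SAP does not state that it will be done that way, and step 3 found no effect. What remains is a gap in specification.

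Fourth, q treats all variance as within-imputation. The between-imputation part is not altered by the fallback, so with missing data q somewhat overstates the effect. The simulations with 20% dropout include this part and still show 6.9–7.2% for SDs 1.8 to 2.1 and about 8% for SDs 1.6 to 2.2.

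**Conclusion.** The point holds conditionally. Two things must happen: the unstructured fit fails, and the Day 365 residual variance differs from the pooled variance. The model-based Day 365 standard error is then wrong, and nothing else in the plan corrects it. For the patterns assumed here, type I error is about 6–11% when variance rises (6.0–6.6% even for a plateau after a lower Day 90), 5.0% when it is constant and about 3% when it falls. The direction and size rest on assumed SDs and correlations, and the simulations also on an assumed 50 per arm and 20% dropout. The simulations used visit-specific baseline slopes, whereas the SAP code has one common slope. The missing one-structure rule is a matter of pre-specification and reproducibility only. This is a free improvement to the plan, not a threat to the primary analysis as it will probably run.

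**What to change.** Replace the fallback sentence in SAP 12.5.1 with a fixed order: heterogeneous Toeplitz, then heterogeneous AR(1), then heterogeneous compound symmetry, keeping DDFM=KR. Use the first that converges in all ten imputed datasets, and use it in every dataset. If none does, use compound symmetry with an empirical (sandwich) standard error and degrees of freedom other than Kenward-Roger, so that the analysis is always defined. Apply the same rule to the worst pain, mITT, PP and subgroup fits of this model.

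The cost is one sentence in the SAP. The largest replacement has 4 variances + 3 correlations = 7 parameters, against the 10 already planned. No data, visits or participants are added, and nothing changes if the unstructured fit converges.
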